# **Protocol Synopsis**

Study title	A randomized, of Phase 2 study to peripheral neuron	assess t						
Protocol number	ART-123 (CIPN	N) - 201						
Study objectives	To assess, under ART-123 for pro- in postoperative pStage II or III of	eventing adjuvan	the ons	et of oxa therapy	aliplati that in	n-induced j	peripheral n liplatin in p	europathy
Clinical phase	Phase 2							
Study design	Multi-center, ran		d, doub	le-blind,	placeb	o-controlle	ed, parallel-	group
Study methodology	This study consiperiod and is of design. After eliundergo 12 cour includes oxaliple subjects will receinfusion over 30 will be allocated receive one dose 2). In the follow observations.  See Appendix T and observations	a placeb gibility of rses of po- atin in the reive AR of minutes to ART e in each r-up period	confirmation ostoperation ostop	olled, do ation in a tive adjusted at the second at the se	uble-b the scr uvant c od. Fro or pla sts and e to re perativ	lind, intergenting period chemotheration Days 1 cebo once dobservation ceive three we adjuvant go the end-	roup compa fod, subjects py (mFOLF to 3 in each daily by int on (Figure 1 doses and to chemothera- of-study tes	FOX6) that a course, ravenous  ). Subjects the other to apy (Figure sts and
	Screening period	1		Treatment pe	riod		Follow-up	J
	(up to 2 weeks)						period (4 weeks)	-
		₩	₩	_₩	~	₩		
		ART-123	1-dose grou	ıp: ART-123	(3 doses)	) /course		
		نٺا	ٺٺا	Jåå.	~	الملا		
	I IC B		1-dose grou	ip: ART-123	(1 dose)			1
	\	(placebo)	(2 doses) /	course ::::	~			
		Placebo gi	,,,	23 (placebo	(3 dose			
	Postoperative adjuvant chemotherapy	L	L	L		L		
	(mFOLFOX6)  L : mFOL  ↓ : ART-	_FOX6 or ·123 386 ·123 (pla	O U/kg acebo)	e (1 dose		eks) (♥:o	xaliplatin)	

[9] Able to sufficiently understand the clinical study and give informed consent

### Exclusion criteria

The presence of any of the following at the time of registration will exclude the patient from this study:

- [1] History of hypersensitivity to any of the ingredients in thrombomodulin alfa (recombinant)
- [2] Peripheral neuropathy or central nervous system (CNS) damage
- [3] Mental disorder of a severity that would affect the efficacy and safety evaluations in this study
- [4] Any treatment history of systemic chemotherapy (including any drug in the clinical trial stage) or radiotherapy intended to provide an anti-tumor effect
- [5] Active double cancer\*1
  - \*1 Synchronous double cancer or metachronous double cancer with disease-free period of no more than 5 years; does not include lesions equivalent to carcinoma in situ or intramucosal carcinoma deemed to have resolved with local treatment
- [6] Yet to recover from an operation or a complication such as a postoperative infection
- [7] Serious intestinal obstruction, diarrhoea, or pyrexia
- [8] History of cerebrovascular disorder (e.g., cerebral haemorrhage, cerebral infarction) within 52 weeks (364 days) before informed consent
- [9] Intracranial haemorrhage, pulmonary haemorrhage, or gastrointestinal haemorrhage (persistent haematemesis/blood in stool or gastrointestinal ulcer-induced haemorrhage)
- [10] Unconfirmed completion of a haemostasis procedure after central nervous system surgery or after trauma
- [11] Receiving transfusion, a blood derivative, G-CSF, or another hematopoietic factor within 7 days before the laboratory tests performed to assess registration eligibility
- [12] Hepatitis B infection and a positive test result for HBs antigen. Patients negative for HBs antigen but positive for HBc or HBs antibody must undergo an HBV-DNA test. A result at or above the normal range will disqualify the patient from enrollment. Test data obtained within 6 months before registration may be used.
- [13] A positive test result for HIV antigen or antibody
- [14] Establishment of an artificial anus (even if temporary) in colorectal cancer surgery
- [15] Administration of another investigational product within 16 weeks (112 days) before informed consent or undergoing observation that is still ongoing a day before informed consent

	T
	[16] Pregnancy or possible pregnancy; wish to become pregnant during the study period; breastfeeding
	[17] Having participated in this study in the past
	[18] Prior treatment history with thrombomodulin alfa (recombinant)
	[19] Is otherwise found unsuited for the study by the investigator or
T	subinvestigator
Investigational	Investigational medicinal product
products	➤ Investigational product code: ART-123
	> Nonproprietary name: Thrombomodulin alfa (recombinant) (JAN)
	➤ A freeze-dried formulation containing 12,800 U thrombomodulin alfa
	(recombinant) per vial
	Control drug (placebo)
	➤ Investigational product code: ART-123 (placebo)
	➤ A freeze-dried formulation free of thrombomodulin alfa (recombinant)
	that is indistinguishable in appearance from ART-123 (the investigational
	medicinal product)
Dose and mode of	Dose and mode of administration
administration and	Administer the investigational product (ART-123 380 U/kg or placebo) once
number of doses of	daily by intravenous infusion over approximately 30 minutes from Days 1 to 3
the investigational	of each course of postoperative adjuvant chemotherapy (mFOLFOX6).
product	[1] ART-123 3-dose group
	On Day 1, initiate ART-123 administration from 2 hours to 30 minutes
	before oxaliplatin administration and complete administration before the
	start of oxaliplatin administration. On Days 2 and 3, administer ART-123
	at about the same time as on Day 1 whenever possible.
	[2] ART-123 1-dose group
	On Day 1, initiate ART-123 administration from 2 hours to 30 minutes
	before oxaliplatin administration and complete administration before the
	start of oxaliplatin administration. On Days 2 and 3, administer the
	placebo at about the same time as on Day 1 whenever possible.
	[3] Placebo group
	On Day 1, initiate placebo administration from 2 hours to 30 minutes
	before oxaliplatin administration and complete administration before the
	start of oxaliplatin administration. On Days 2 and 3, administer the
	placebo at about the same time as on Day 1 whenever possible.
	Criteria for suspension/resumption of the investigational product
	Suspend use of the investigational product when the administration of
	oxaliplatin, as a part of the postoperative adjuvant chemotherapy, is suspended.
	Resume investigational product administration concurrently with the resumption

	of oxaliplatin administration.
	Number of doses 36 (three/course × 12 courses)
Dose and mode of	Administer mFOLFOX6 as postoperative adjuvant chemotherapy.
administration of	See Section 8.3 for the specific doses, administration procedures, and dosing
standard	schedule.
concomitant	
medications	
Treatments	Prohibited concomitant medications
prohibited during	➤ The administration of the following medications is prohibited from
the study	informed consent until study completion.
	(1) Other investigational products
	(2) Thrombomodulin alfa (recombinant)
	(3) Antineoplastic agents other than those specified for use in the
	postoperative adjuvant chemotherapy in this study
	➤ The administration of the following medications is prohibited from the
	start of administration of the investigational product until study
	completion.
	(1) Thrombolytic drugs (e.g., t-PA preparations, urokinase)
	Restricted concomitant medications
	Over-the-counter medications and ready-made transfusion preparations are not
	considered restricted concomitant medications.
	➤ The administration of the following medications is prohibited from
	informed consent until study completion except in association with use
	while peripheral motor neuropathy or peripheral sensory neuropathy is
	found by the investigator or subinvestigator to be Grade 2 or greater
	based on National Cancer Institute-Common Terminology Criteria for
	Adverse Events version 4.0 (NCI-CTCAE).
	(1) Calcium gluconate, magnesium sulfate
	(2) Glutathione
	(3) L-glutamine
	(4) Vitamin B 6 , B 12 , and E preparations
	(5) Goshajinkigan, shakuyaku-kanzoto
	(6) Narcotics and similar drugs (including the opioid receptor agonist codeine phosphate)
	(7) Oral and injected adrenocorticosteroids (except when used to treat
	nausea/vomiting associated with the administration of an
	antineoplastic agent or to treat an allergy)
	(8) Pregabalin, gabapentin
	(o) i regavann, gavapenun

- (9) Nonsteroidal anti-inflammatory drugs (NSAIDs, except when used for a purpose other than chemotherapy-induced peripheral neuropathy [CIPN] treatment)
- (10) Tricyclic antidepressants
- (11) Serotonin/noradrenaline reuptake inhibitors
- ➤ Initiating the administration of or increasing the dose of any of the following medications is prohibited from informed consent until study completion. Subjects may continue to use the medications that they had been using before informed consent provided that no dose changes are made. (Dose reductions are allowed.)
  - (1) Isoniazid, ethambutol, metronidazole, medications for the treatment of HIV infection, HMG-CoA reductase inhibitors, tacrolimus, colchicine, and interferon preparations

## **Prohibited therapies**

- ➤ The following treatments are prohibited from informed consent until study completion.
  - (1) Radiotherapy
  - (2) Operations and other surgical procedures that could affect efficacy evaluation

## **Endpoints**

### Efficacy

- [1] NCI-CTCAE peripheral motor neuropathy, peripheral sensory neuropathy (CIPN only)
- [2] DEB-NTC
- [3] FACT/GOG-NTX-12
- [4] FACT-G
- [5] Numerical rating scale (NRS) (pain)
- [6] Discontinuation, suspension, and dose reduction of oxaliplatin due to CIPN

The efficacy endpoints will not be classified as primary or secondary because this is an exploratory study of ART-123 in prevention of the onset of oxaliplatin-induced peripheral neuropathy.

## Safety

- [1] Vital signs (body temperature, blood pressure systolic/diastolic, pulse rate)
- [2] Laboratory tests (routine blood tests, clinical chemistry tests, urine analysis, coagulation tests)
- [3] Immunogenicity (anti-drug antibodies, neutralising antibodies)
- [4] Adverse events other than CIPN

	Pharmacokinetics
	Blood concentration of thrombomodulin alfa (recombinant)
Treatment and	Screening period: up to 14 days
observation periods	Treatment period: 24 weeks (up to 36 weeks)
	Follow-up period: 4 weeks (up to 6 weeks)
Target sample size	75 subjects (25 per group)
Study period	July 2016 to January 2018
Primary analysis	[1] Analysis set
methods	The primary efficacy analysis set is the full analysis set (FAS).
	[2] Handling of primary efficacy data
	Handling of missing data on whether an assessment is NCI-CTCAE
	Grade 1 or greater
	Consider subjects for whom these data are missing to have had an
	NCI-CTCAE Grade 1 or greater event. Perform sensitivity analysis
	that includes analysis with a missing NCI-CTCAE grade for all such
	subjects.
	Handling of NCI-CTCAE evaluation data in the second and
	subsequent courses
	Evaluate the Day 1 (baseline) NCI-CTCAE grades as those from
	the immediately preceding course. Evaluate the Days 2, 3, 15, and 29
	NCI-CTCAE grades as those observed within the course.
	Handling of missing efficacy endpoint data (continuous variables)
	Do not impute missing continuous efficacy endpoint data. Perform
	sensitivity analyses with imputation using the
	last-observation-carried-forward (LOCF) approach.
	[3] General matters pertaining to efficacy analysis
	This study is conducted to assess and characterize the clinical effect of
	ART-123 for preventing the onset of oxaliplatin-induced peripheral
	neuropathy and to explore appropriate efficacy indices. Thus, efficacy
	analyses will be performed primarily with descriptive statistics obtained
	by summarizing and graphing data from each evaluation time point.
	The incidences of NCI-CTCAE Grade 1 or greater events will be
	evaluated with statistical tests and 95% confidence intervals as necessary
	in addition to descriptive statistics to allow intergroup comparison. The
	incidences of NCI-CTCAE Grade 1 or greater events with
	discontinuations and dropouts factored in will also be estimated.
	The significance level is set at 5% (two-sided), with a two-sided
	confidence interval and a confidence coefficient of 95%. Given the
	exploratory nature of the study, multiplicity will not be adjusted for.

Appendix Table 1 Summary of study schedule

							A	pper	naix	able	15	umm	nary (	or stu	lay s	cnec	lule								_	Remova S	_
	Screening period											T	reatmen	t period	ı											Follow-up period h)	
	-	Course 1					ev -					Courses	2 to 11						C			evaluation					
Test/observation schedule			Investigational product administration		D2	D3			D29	20	Investigational product administration administration	urse)	D2 a)	D3 a)	D8	D15	D29	prece	Investigational product administration administration	urse)	D2 a)	D3 a)	D8	D1 5	At discontinuation of the treatment 	At study completion (d43 of the last course) 	Unscheduled CIPN eval
Permitted window of time from the specified date (days)	d-14 to d-1				-		ē	+7	+7	100000000	d43 of eding co		-	·		+7	+7		d43 of eding co		-		ē	+7	-	+14	-
Written informed consent																											
Subject demographic information survey	•	•																									
Patient registration, randomization													80 80	08		80	38										
Office visit	•				•	•		0	0		•	_	•	•		0	0		•		•	•			•	•	•
Weight measurement		•k)								•k)								•k)									
Investigational product administration					•	•					a )		•	•					•a)		•	•					
Investigational product administration status survey			•		•	•		0	0		•		•	•		0	0		10		•	•					
Postoperative adjuvant				Ū		$\uparrow$						—		1	90					+		$\rightarrow$					
chemotherapy																											
Postoperative adjuvant chemotherapy status survey				•	•0	•0		0	0			•	•0	•)		0	0			•	•j)	•D					
Concomitant medications/concomitant therapies survey	←																							→		•	
Pregnancy test										•d)			100			1-										•	
NCI-CTCAE		•			•	•		0	0	•			•	•		0	0	•			•	•		•	•	•	•
DEB-NTC		•				9		0	0	•			- 80			0	0	•	9.					•	•	•	
DEB-NTC FACT/GOG-NTX-12		•				, i	•	0	0	•	2		2		٠	0	0	•					•	•	•	•	
FACT-G		•								•e)			100	70		100	08							•	•	•	

	NRS (pain)		•				•	0	0	•				•	$\circ$	$\circ$	•				•	•	•	•	
	Laboratory tests	•°)								• k)							• k)					•	•	•	
ety	Vital signs	•								٠							•					•	•	•	
Saf	Adverse events	4																				ļ	•	•	
	Adverse events	•																					•		
	Immunogenicity		•																					•	
Ph	rmacokinetics		•	• f)	• f)	• f)						$\Delta^{f)}$	$\Delta^{f)}$				·		$\Delta^{f)}$	$\Delta^{f)}$	•				

Time points are expressed as "Day (D)," and numbers of days are expressed as "day (d)."

- •: required
- : to be performed only in the event of postponement of the administration of all drugs for postoperative adjuvant chemotherapy
- Δ: if no blood samples are available from course 1, perform once in one of the courses from 2 to 12
- a) Not required in courses in which oxaliplatin is suspended
- b) To be performed before investigational product administration if efficacy and safety evaluations take place on the same day as investigational product administration
- c) To be performed between Day -7 and Day -1 (1 day before registration); hepatitis B test data obtained within 6 months before the day of registration may also be used
- d) To be performed only in course 2; may be determined on the day before Day 1
- e) To be performed only in courses 5 and 9
- f) Collect blood samples immediately after and from 30 to 120 minutes after completion of investigational product administration
- g) If the evaluation at treatment period discontinuation takes place on or after Day 43 of the last course of postoperative adjuvant chemotherapy, or if the subsequent tests/observations for the study are not possible, perform the end-of-study evaluations instead of the treatment-period discontinuation evaluations. If the course 12 postoperative adjuvant chemotherapy has not commenced within 34 weeks (Day 239 from the day of registration), discontinue the subject from the study, perform the treatment-period discontinuation evaluations, and then perform the end-of-study evaluations on Day 43 of the last course of postoperative adjuvant chemotherapy.
- h) If any postoperative adjuvant chemotherapy for the subsequent course has not commenced by Day 43 of a course, discontinue the subject from the study and perform the end-of-study evaluations.
- i) If the subject is discontinued from the study in the follow-up period, perform the end-of-study evaluations
- j) Determine the status of fluorouracil continuous intravenous infusion use
- k) May be determined on the day before Day 1

## List of general abbreviations

Abbreviation	Unabbreviated expression
ART-123	Thrombomodulin alfa (recombinant)
Recomodulin	A drug product containing thrombomodulin alfa (recombinant) as the active pharmaceutical ingredient (proprietary name: Recomodulin® Inj. 12800)
CIPN	Chemotherapy-Induced Peripheral Neuropathy
DEB-NTC	Neurotoxicity Criteria of DEBIOPHARM
ECOG	Eastern Cooperative Oncology Group
EDC	Electronic Data Capture
FACT	Functional assessment of Cancer Therapy
FACT-G	Functional Assessment of Cancer Therapy-General (Version 4)
FACT/GOG-NTX-12	Functional Assessment of Cancer Therapy/Gynecologic Oncology Group-Neurotoxicity (Version 4)
FAS	Full analysis set
GCP	Good clinical practice
G-CSF	granulocyte-colony stimulating factor
HBV	Hepatitis B virus
HIV	Human Immunodeficiency Virus
HMG-CoA	hydroxymethylglutaryl-CoA
IWRS	Interactive Web Response System
LOCF	Last Observation Carried Forward
mFOLFOX6	modified FOLFOX6
NCI-CTCAE	National Cancer Institute Common Terminology Criteria for Adverse Events ver.4.0
NRS	Numerical rating scale
PPS	Per protocol set
pStage	pathological Stage
QOL	Quality of life
TEAE	Treatment-emergent adverse event
TM	thrombomodulin
t-PA	tissue-plasminogen activator

## List of laboratory test abbreviations

Abbreviation	Description of abbreviation
AL-P	Alkaline phosphatase
ALT (GPT)	Alanine aminotransferase (glutamic pyruvic transaminase)
AST (GOT)	Aspartate aminotransferase (glutamic oxaloacetic transaminase)
BUN	Blood urea nitrogen
Cl	Chlorine
HBc	Hepatitis B core
HBs	Hepatitis B surface
K	Potassium
LDH	Lactate dehydrogenase
Na	Sodium
PT-INR	prothrombin time international normalized ratio

## 1. Background Information and History of Development

## 1.1 Background Information

## 1.1.1 Epidemiology and Treatment of Colorectal Cancer

An estimated 136,000 people in Japan were diagnosed with colon cancer in 2015, and the number of afflicted people is growing (2015 estimate of National Cancer Center Japan). Treatment options such as endoscopic treatment, surgery, chemotherapy, and radiotherapy are selected according to how advanced the disease is. Rapid advances in antineoplastic agents have made chemotherapy an option comparable in benefit to surgery and radiotherapy. Chemotherapy, however, must sometimes be modified or discontinued because of the adverse reactions it causes.

## 1.1.2 Overview of Chemotherapy-induced Peripheral Neuropathy

Chemotherapy-induced peripheral neuropathy (CIPN) is one adverse reaction that can affect whether chemotherapy can be continued. Symptoms of CIPN include numbness, abnormal sensations, and hypoaesthesia of the extremities caused by sensory nerve damage and muscular atrophy and muscular weakness caused by motor nerve damage. CIPN varies in incidence from drug to drug, occurring most frequently in association with the antineoplastic agent oxaliplatin, which is a platinum compound, followed by the taxane drug paclitaxel.

## 1.1.3 Oxaliplatin-induced Peripheral Neuropathy

Oxaliplatin-induced peripheral neuropathy takes the forms of acute peripheral neuropathy, which appears just after to several days after oxaliplatin administration, and chronic peripheral neuropathy, which appears later over the course of oxaliplatin treatment. Temporary numbness and abnormal sensations in the limbs and mouth, one manifestation of acute peripheral neuropathy, affect almost everyone (85% to 95%) treated with oxaliplatin. Manifestations of chronic peripheral neuropathy include persistent numbness and abnormal sensations of the limbs, fine-motor impairments such as difficulty buttoning clothing, and movement disorders such as difficulty walking. The risk of these conditions increases as the cumulative dose of oxaliplatin increases. These conditions, moreover, substantially reduce patient quality of life (QOL). The modification and discontinuation of chemotherapy caused by chronic peripheral neuropathy is particularly clinically significant .

Although the specific mechanism of the onset of oxaliplatin-induced peripheral neuropathy remains uncharacterized, chronic peripheral neuropathy is attributed to axonal degeneration resulting from nerve cell body damage. Because damaged nerves require a long time for repair, symptoms may persist for several months or years after the end of oxaliplatin treatment. Preventing the onset of oxaliplatin-induced peripheral neuropathy is therefore important.

## 1.1.4 Status of CIPN Prevention and Treatment

No drug indicated for preventing the onset of or treating CIPN is available in Japan or elsewhere. In Japan, CIPN is empirically treated with products including calcium-magnesium formulations, carbamazepine, gabapentin, pregabalin, and Chinese herbal medications (goshajinkigan), although

sufficient evidence supporting their use is lacking, and efficacy has not been demonstrated. Oxaliplatin dose reduction or suspension is therefore performed as symptomatic treatment for CIPN. The American Society of Clinical Oncology published a guideline on the prevention and management of CIPN in 2014. The guideline recommends only duloxetine for treating CIPN and has no recommended pharmacotherapies for preventing onset.

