# 8.4.2 Restricted Concomitant Drugs

Over-the-counter medications and ready-made transfusion preparations are not considered restricted concomitant medications.

> The administration of the following medications is prohibited from informed consent until study completion except in association with use while peripheral motor neuropathy or peripheral sensory

neuropathy is found by the investigator or subinvestigator to be Grade 2 or greater based on NCI-CTCAE.

- (1) Calcium gluconate, magnesium sulfate
- (2) Glutathione
- (3) L-glutamine
- (4) Vitamin B6, B12, and E preparations
- (5) Goshajinkigan, shakuyaku-kanzoto
- (6) Narcotics and similar drugs (including the opioid receptor agonist codeine phosphate)
- (7) Oral and injected adrenocorticosteroids (except when used to treat nausea/vomiting associated with the administration of an antineoplastic agent or to treat an allergy)
- (8) Pregabalin, gabapentin
- (9) Nonsteroidal anti-inflammatory drugs (NSAIDs, except when used for a purpose other than CIPN treatment)
- (10) Tricyclic antidepressants
- (11) Serotonin/noradrenaline reuptake inhibitors

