#### Rationale

- For ethical reasons, prohibitions of these medications are lifted because NCI-CTCAE Grade 2 or greater peripheral motor neuropathy or peripheral sensory neuropathy is of a severity requiring consideration of oxaliplatin dose reduction/suspension.
- (1) to (5) These drugs are reported to be effective in the prevention or treatment of CIPN, meaning that their use would prevent proper evaluation of efficacy.
- (6) to (11) These drugs may be effective in the treatment of CIPN, meaning that their use would prevent proper evaluation of efficacy.
- ➤ Initiating the administration of or increasing the dose of any of the following medications is prohibited from informed consent until study completion. Subjects may continue to use the medications that they had been using before informed consent provided that no dose changes are made. (Dose reductions are allowed.)
  - (1) Isoniazid, ethambutol, metronidazole, medications for the treatment of HIV infection, HMG-CoA reductase inhibitors, tacrolimus, colchicine, and interferon preparations

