#### 9.3 Subject Demographic Information Survey

The investigator or subinvestigator will determine the following information and enter it in the eCRF.

- > Initially assigned drug number
- > Day of registration
- ➤ Body height and weight (date of measurement and values), smoking status, drinking status and alcohol consumption
- > ECOG performance status
- ➤ Details of colon cancer (site [cecum/ascending colon/transverse colon/descending colon/sigmoid colon/rectosigmoid], disease stage [I/II/IIIa/IIIb/IV], date of resection)
- ➤ Comorbidities: disease(s) present at informed consent
- ➤ History: history of peripheral neuropathy (disease name, time of disease), history of CNS neuropathy (disease name, time of disease), history of diabetes mellitus (disease name, time of disease), history of alcohol abuse (time of disease)
- ➤ Details of menopause\*1 (premenopausal or <2 years since menopause/≥2 years since menopause)
  \*1 Female subjects only

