#### 9.5.1.1 Concomitant Medications that are Neither Prohibited nor Restricted

• Name of drug, first day of administration, last day of administration

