#### 9.5.1.2 Prohibited and Restricted Concomitant Medications

The information listed below will be determined for any prescription drug used that corresponds to the definition of a prohibited or restricted medication, even if the route of administration and the reason for its use are in compliance. Over-the-counter medications and ready-made transfusion preparations are considered concomitant medications described in "9.5.1.1 Concomitant medications that are neither prohibited nor restricted."

• Name of drug, route of administration, first day of administration, last day of administration, dose, reason for administration (CIPN/adverse event/other)

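### Carbamazepine, named in Section 1.1.4 as an empirical CIPN treatment, is left off the restricted-drug lists without a reason

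*Protocol*

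**What the plan says.** Protocol Section 1.1.4, on current practice in Japan, states that "CIPN is empirically treated with products including calcium-magnesium formulations, carbamazepine, gabapentin, pregabalin, and Chinese herbal medications (goshajinkigan"). It adds that evidence for these products is insufficient and that efficacy has not been shown, and it makes no distinction among the five.

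The first restricted list in Section 8.4.2, repeated in the synopsis, has 11 items. They are barred from consent to study completion except while motor or sensory neuropathy is Grade 2 or worse. The list includes calcium gluconate and magnesium sulfate (item 1), goshajinkigan (item 5) and "8) Pregabalin, gabapentin" (item 8). Item (9) has an exception by purpose: "Nonsteroidal anti-inflammatory drugs (NSAIDs, except when used for a purpose other than CIPN treatment"). For items (6) to (11) the rationale is: "These drugs may be effective in the treatment of CIPN, meaning that their use would prevent proper evaluation of efficacy".

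What is recorded depends on the list. For drugs that are neither prohibited nor restricted, Section 9.5.1.1 asks for "Name of drug, first day of administration, last day of administration". For prohibited and restricted drugs, Section 9.5.1.2 asks for "Name of drug, route of administration, first day of administration, last day of administration, dose, reason for administration (CIPN/adverse event/other"), and it does so "even if the route of administration and the reason for its use are in compliance". Under Section 9.2.5, only the prescription of a restricted drug for CIPN triggers an unscheduled evaluation.

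**The concern.** The protocol identifies carbamazepine as a drug that Japanese physicians use for CIPN, and then leaves its use for CIPN uncontrolled below Grade 2. The reason for use is not collected either.

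Carbamazepine started after a first Grade 1 event cannot undo that event. If it relieves symptoms, it could affect:

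- the incidence of Grade 2 or worse neuropathy and the incidence by course (Section 12.6.2.1);
- the patient-reported neurotoxicity and pain scores (Sections 12.6.2.3 and 12.6.2.5);
- oxaliplatin modification due to CIPN (Section 12.6.2.6), because the Day 1 grade drives dose reduction and suspension (Table 8.3-5).

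Allocation is randomized and blinded, so use would not be driven by knowledge of the arm. It could still be driven by symptoms. If ART-123 works, placebo subjects would have more symptoms and might receive more co-treatment, which would tend to shrink the observed difference.

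**Working it through.** The plan states no figure on this point. The check is a comparison of lists, then of record fields, then of what the assessment schedule recovers.

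**1. Products named in Section 1.1.4 against the lists in Section 8.4 and the synopsis**

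| Product | Place in the restricted list |
|---|---|
| Calcium-magnesium | item (1) |
| Goshajinkigan | item (5) |
| Gabapentin | item (8) |
| Pregabalin | item (8) |
| Carbamazepine | none |

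Named: 5. Listed: 4. Missing: 5 − 4 = 1.

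Duloxetine, which Section 1.1.4 mentions as a guideline recommendation, falls under item (11), serotonin/noradrenaline reuptake inhibitors. Carbamazepine has no such cover: the list has no anticonvulsant class, and gabapentin and pregabalin are listed by name. It is also absent from the prohibited drugs in Section 8.4.1 and from the second list in Section 8.4.2, which bars starting or increasing drugs that may themselves cause neuropathy.

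**2. Record fields**

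- Section 9.5.1.1: name, first day, last day = 3 items.
- Section 9.5.1.2: name, route, first day, last day, dose, reason = 6 items.
- Not collected for carbamazepine: 6 − 3 = 3 (route, dose, reason).

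Use for CIPN would have to be inferred from the start date, the dated grades, the adverse events and the baseline survey in Section 9.3 ("Comorbidities: disease(s) present at informed consent").

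**3. What the missing Section 9.2.5 trigger costs**

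Scheduled NCI-CTCAE assessments (Section 9.6.3.1), assuming no postponement, suspension or discontinuation:

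- Days 1, 2 and 3 in 12 courses: 3 × 12 = 36
- Day 15 of course 12: 36 + 1 = 37
- study completion: 37 + 1 = 38

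All except Day 1 of course 1 record the worst grade since the preceding scheduled assessment: 38 − 1 = 37. The longest nominal gap on treatment is Day 3 to Day 15, the next Day 1: 15 − 3 = 12 days. Little is therefore lost through the missing trigger, mainly the grade at the moment of prescribing.

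These counts locate the gap. They do not measure bias.

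**The case against.** The strongest reply is that no rule is broken. Section 1.1.4 is background and does not promise that every product it names will be restricted. The criterion for listing is possible or reported efficacy, not empirical use, and Section 1.1.4 itself says that efficacy is unproven. It is correct that two rules do not conflict here. Unproven efficacy does not explain the omission, though, because the same sentence covers the four products that are restricted, and the threshold for items (6) to (11) is only that a drug may be effective.

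A second reply is that the list was never watertight. Over-the-counter products are exempt, two items (7 and 9) carry exceptions by purpose, and everything on the list is allowed from Grade 2. That is so, but the over-the-counter exemption does not extend to a prescription drug, and the other tolerances are stated openly.

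A third reply is that users stay identifiable by name and dates. Carbamazepine started on treatment with no matching comorbidity or adverse event could be counted conservatively as use for CIPN. This stands, and it limits the harm. The attribution would still be a judgement, and a statistical analysis plan cannot recover a reason that was never collected.

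Finally, no effect on the results is shown. That also stands: the study is exploratory, has no primary endpoint and is mainly descriptive.

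**Conclusion.** The point holds as a minor one. Carbamazepine is the only one of the five products named in Section 1.1.4 as empirical CIPN treatment that is missing from the restricted lists. The protocol gives no reason, and by its own rationale the drug belongs there. The consequence is permitted use for CIPN below Grade 2, with the reason for that use unrecorded.

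The effect on the results is probably small and cannot be quantified, because the protocol gives no figure for how often carbamazepine would be used or what it would do. No sample size, power or significance level depends on it. Any bias requires that carbamazepine is actually prescribed for CIPN before Grade 2 and that it alters symptoms or their grading. The protocol establishes neither.

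**What to change.** Add *(12) Carbamazepine* to the first restricted list in Section 8.4.2 and in the synopsis, with the exception by purpose that item (9) has for NSAIDs. In the Section 8.4.2 rationale, change the range (6) to (11) to (6) to (12). The Grade 2 rule and the Section 9.2.5 evaluation then apply to use for CIPN. Section 9.5.1.2 captures the reason for every use, including permitted use for another condition.

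Item (8) is the closer pharmacological neighbour and has no such exception. Copying it would force a patient who takes carbamazepine for something else to stop. With the reason recorded, that stricter form is not needed.

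The cost is one item in two lists, one number in the rationale, and 3 more fields per carbamazepine record in an existing eCRF form. No patient on carbamazepine for another condition is excluded. If the drug was left out on purpose, a sentence in the rationale giving the reason would settle the point.
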